## **Objectives**

### **Primary:**

- 1 - Control of radiological disease at 6 months after the end of treatment.
- 2- Control of clinical/biochemical (functional NET) at 6 months after the end of treatment.

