## **Outcomes**

### **Primary:**

Disease control rate (DCR). Defined by absence of radiological progression in conventional imaging examinations by RECIST 1.1 at 6 months after the end of treatment. For patients with functioning syndrome, beside radiological DCR, patients should have improved in at least 10% of the baseline score of quality-of-life (EORTC QLQ-GINET21) and stability or decrease in tumor markers.

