#### Quality of Life Assessment:

The quality-of-life assessment will be conducted by two questionnaires from the European Organization for Research and Treatment of Cancer Quality of Life Questionnaire group, composed of the general questionnaire EORTC QLQ-C30 and its specific domain for TNE, the QLQ-GINET21, both available in Portuguese of Brazil by cross-cultural validation.

The QLQ – C30 general quality of life questionnaire was developed for cancer patients and is one of the most used in clinical cancer research, having already been applied by more than 80,000 cancer patients. Version 3 is the one currently used. It is

multidimensional, can be self-administered and consists of 30 questions that assess the patient in the last two weeks. The questionnaire addresses general questions about cancer, such as symptoms, side effects of treatment, psychological suffering, physical functioning, social interaction, sexuality, body image, global health, quality of life and satisfaction with medical care, regardless of the type of cancer. It is a generic quality of life document for cancer, composed of 30 questions that define the general quality of life, through five functional scales (physical, role/performance, cognitive, emotional and social), three symptom scales (fatigue, pain and nausea/vomiting) and six simple items (dyspnea, insomnia, loss of appetite, constipation, diarrhea and financial difficulties).

The scale in this questionnaire constitutes the following score: 1 (no), 2 (little), 3 (moderately), and 4 (a lot), except the global health scale. This consists of 2 questions that ask the individual to rate their general health and quality of life in the last week, through a score from 1 to 7, 1 being terrible and 7 being excellent. Scores are calculated separately for each of the scales (functional, QOL and symptoms), ranging from zero - 100. On the Global Health and functionality scale, the higher the score, the better the quality of life. In the symptom scales, the higher the score, the worse the score. In order to know the calculation in each scale, the average score in each of the scales is performed. After this average we make the linear transformation for the score to be 0-100, according to the formulas below:

- Gross score or Raw Score (RS): adds the score of each item and divides it by the number of items

- S score for functional scales:  $\{1 - (RS - 1) / \text{variation}\} \times 100$

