- S score for symptom scale:  $\{(RS - 1) / \text{variation}\} \times 100$

- S-score for general health status / general quality of life:  $\{(RS - 1) / \text{variation}\} \times 100$

The variation is generally 3, since the items score from 1 to 4, except for the global health and quality scales that score a maximum of 7 and, therefore, there is a general variation of 6.

The complement of the QLQ-C30 for TNE, the QLQ-GINET21 questionnaire, is composed of 5 multi-item scales that address common symptoms in patients with NET, such as gastrointestinal and endocrine, concerns about illness, social role and symptoms of treatments; it also contains five items that assess weight loss/gain, bone/muscle pain,

sexual function. The methodology for calculating the scores is the same as that used by the questionnaire QLQ-C30.

Missing data often occurs in questionnaire studies. Researchers will try to minimize missing data by providing guidance to study participants. However, if it still occurs, several imputation methods can be used, and there is no standard method. The most common is to calculate the average of the scale of the answered items and use this average to input the missing value, provided that at least 50% of the items of that scale have been answered. This will be the method used in this study to treat possible missing data. When missing data occurs in single items, they should be excluded from the analysis.

The EORTC quality of life questionnaires will be applied at the baseline (within 4 days of treatment) and every 12 weeks (window of +/- 5 days) until the study leaves. The administration should preferably be on the day of the image, and always before the patient knows the result of the exam (so that the result does not influence the responses to the questionnaires) and by a trained investigator.

The total time to complete the QLG-C30 and LQL-GINET21 is approximately 20 to 30 minutes. The patient himself will complete the questionnaires; however, he may be helped by an investigator, if in doubt. In the end, it will be inserted in a closed envelope to ensure confidentiality and privacy.

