### **Statistical plan**

Descriptive statistics will be used to report population characteristics, binary outcomes and adverse events. The Kaplan-Meier method will be used to report time-to-event variables and the reverse Kaplan-Meier method will be used to calculate the follow-up time for patients. For the analysis of quality of life, we will report the proportion of patients who increase the sum of the total score by at least 10% at 3 and 6 months after treatment - improvement of at least 10% is considered to be clinically significant by patients. We will also evaluate whether the global score varies and how much varies during the study for each patient; this analysis will be carried out in percentage and descriptively. The scores will be calculated according to the instruction manual of the EORTC group. The quality-of-life analysis will be carried out using the

intention to treat method, where patients who do not respond will be considered “non-responders” in terms of the effectiveness of the treatment.

Missing data in the questionnaires will be dealt with as described in the section above "Quality of Life Assessment".

The study sample will be 22 patients. For this calculation, we considered the 40-month disease control rate H0 to be 40% (placebo arm of phase III studies in TNE, such as the RADIANT417 study), H1 to 67%. Two-tailed type I error margin of 10%, power of 80% and loss of follow-up / non-adherence of 10% were considered.

We estimated a 40% screening failure (40% positivity on MIBG-I131).

All analyzes will be by intention to treat. Patients who receive at least one dose of MIBGI131 will be evaluated for toxicity and efficacy.

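### In functional NET, clinical control rests on an unspecified GINET21 score; if the whole score is meant, non-hormonal change can decide the result, so the hormonal scales should be named in advance

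*Combined protocol and SAP*

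**What the plan says.** The second primary objective is "Control of clinical/biochemical (functional NET) at 6 months after the end of treatment". The primary outcome (Outcomes, Primary) puts this into operation for patients with a functioning syndrome: besides no RECIST 1.1 progression, "patients should have improved in at least 10% of the baseline score of quality-of-life (EORTC QLQ-GINET21) and stability or decrease in tumor markers". Item 1 of the secondary outcomes repeats the same condition at 3 months. Neither place says which GINET21 score is meant.

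The Statistical plan, in its sentence on the quality-of-life analysis, reports "the proportion of patients who increase the sum of the total score by at least 10% at 3 and 6 months after treatment". The Quality of Life Assessment section describes scoring differently: "Scores are calculated separately for each of the scales (functional, QOL and symptoms), ranging from zero - 100", with the same method applied to GINET21. It lists the instrument's five multi-item scales as covering "common symptoms in patients with NET, such as gastrointestinal and endocrine, concerns about illness, social role and symptoms of treatments", and adds that "it also contains five items that assess weight loss/gain, bone/muscle pain" and sexual function. On direction it says: "In the symptom scales, the higher the score, the worse the score".

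Under Study design, symptoms are assessed through the quality-of-life questionnaires. Table 2 schedules a separate signs and symptoms assessment, but no outcome uses it.

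**The concern.** The objective is control of a hormone syndrome. The measure is a questionnaire in which, on the protocol's own description, at most two of five scales (endocrine and gastrointestinal) plausibly reflect that syndrome. The other three scales concern illness worries, social role and treatment symptoms, and the single items cover weight, bone or muscle pain and sexual function.

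The GINET21 condition is necessary for success in every functional patient. The marker condition does not close the gap, because stability is enough. If the criterion is read on the whole score, a functional patient can be classified by changes unrelated to the syndrome, in either direction. Quality of life is already a separate secondary outcome (item 5) with the same questionnaire and the same 10% threshold, so the primary endpoint has no distinct measure of the syndrome's symptoms.

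**Working it through.** **The plan's own figure.** The only related figure is the sample size, and it reproduces. With H0 40%, H1 67%, two-sided 10% and 80% power:

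n = [1.645 × √(0.40 × 0.60) + 0.842 × √(0.67 × 0.33)]² / 0.27² = 19.8, and 19.8 / 0.9 = 22.0.

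This point does not change it.

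**Inputs.** The 10% threshold comes from Outcomes, Primary. The five scales and five single items come from Quality of Life Assessment. The documents give no items per scale, no weights and no baseline scores, so those below are assumptions. All scores are taken as 0–100 with higher meaning worse.

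**General rule.** Let s be the hormonal share of the baseline total.

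- Hormonal part halved, rest unchanged: the total improves by s/2. This is under 10% when s < 20%.
- Hormonal part unchanged: the total reaches 10% when the rest falls by 0.10/(1 − s). That is 11.1% for s = 0.10, 12.5% for s = 0.20 and 16.7% for s = 0.40.
- Hormonal part halved, rest worsening: the criterion fails when the rest rises by more than (s/2 − 0.10)/(1 − s). For s = 0.40 that is 0.10/0.60 = 16.7%.

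**Passing with hormonal symptoms unchanged.**

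- Five scales, in the order endocrine, gastrointestinal, worries, social, treatment: 40/40/60/50/30 becomes 40/40/45/40/30. The sum goes from 220 to 195, and 25/220 = 11.4%: improved.
- Ten equal scores, endocrine unchanged at 66.7 and the others at 33.3, with two non-hormonal scores falling to 0: the sum goes from 366.4 to 299.8, and 66.6/366.4 = 18.2%: improved. For a single item, 33.3 to 0 is one response step.

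**Failing although hormonal symptoms fall.** Baseline is 66.7 on each scale that is halved and 33.3 on all others:

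| Weighting | What is halved | Mean before | Mean after | Improvement | Result |
|---|---|---|---|---|---|
| Ten equal scores | Endocrine | (66.7 + 9 × 33.3)/10 = 36.64 | 33.31 | 9.1% | fails |
| Five scales | Endocrine | (66.7 + 4 × 33.3)/5 = 39.98 | 33.31 | 16.7% | passes |
| Ten equal scores | Endocrine and gastrointestinal | (2 × 66.7 + 8 × 33.3)/10 = 39.98 | 33.31 | 16.7% | passes |

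The shares explain the pattern: 66.7/366.4 = 18.2% in the first row, 66.7/199.9 = 33.4% in the second, and 133.4/399.8 = 33.4% in the third.

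Worsening elsewhere can also produce a failure. If 40/40/60/50/30 becomes 20/20/70/55/45, both hormonal scales have halved, yet the sum goes from 220 to 210, an improvement of only 4.5%.

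**The case against.** **The whole-score reading is not certain.** A reader might infer that the plan decides control on the total GINET21 score. The documents do not establish this. The outcome definition says only baseline score. The summed total appears in a sentence about the quality-of-life analysis, and scoring by scale is described elsewhere. This stands: the certain defect is that the score is not specified. But nothing links the 10% rule to any scale, and the total is the only computation stated, so the text needs changing under either reading.

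**The failing case is fragile.** A reader might infer that halved hormonal symptoms will usually fail. They will not. The 9.1% result needs ten equal weights and a fall in the endocrine scale alone; the other two rows of the table pass. This also stands. Failure is possible but conditional.

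**Side effects are a weak argument.** The treatment-symptom scale might seem to bring toxicity into the efficacy endpoint. The primary reading is 6 months after treatment ends, while Study design says toxicities usually resolve about 30 days after treatment. I do not rely on it.

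**Unchanged symptoms may be control.** With no radiological progression and stable markers, unchanged symptoms could be called control. But the protocol itself requires improvement on the questionnaire, so improvement in unrelated domains should not satisfy that requirement.

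**Overall benefit is a defensible target.** The protocol assigns symptom assessment to the questionnaires on purpose. However, the Hypotheses section names symptomatic control and improved quality of life separately, and the latter already has its own outcome.

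**Conclusion.** The mismatch between objective and measure is real, and it is conditional on the whole score being used. In that case the passing direction is robust: a fall of 11.1% to 16.7% in the non-hormonal part is enough, for hormonal shares of 10% to 40%, provided the radiological and marker conditions are met. The failing direction holds only when the hormonal share is small (below 20% for a halving with nothing else changing) or when other scales worsen.

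The effect on the disease control rate cannot be computed, because the share of functional patients is not given. For scale only, one misclassified patient among 22 moves the rate by 1/22 = 4.5 points, against a 27-point gap between H0 and H1. It would go too far to say that the disease control rate fails its objective as a whole: the condition does not apply to non-functional patients. This is a worthwhile low-cost improvement that leaves the design and sample size unchanged.

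**What to change.** In Outcomes, Primary, and in item 1 of the secondary outcomes:

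- Judge the functional criterion on the GINET21 endocrine and gastrointestinal scales. Name them in advance and say how they are combined.
- State that a lower score means improvement. The Statistical plan counts an increase in the total, which is the wrong direction for symptom scales.
- State how a patient with a baseline of 0 on these scales is counted, since such a patient cannot improve by 10%.
- Keep the remaining scales and items for secondary outcome 5.

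The cost is wording only, because the data are already collected and scored by scale. There are three drawbacks. Fewer items give a coarser score. One response step may reach 10%: if a scale had three items (an assumption), one step would be 100/(3 × 3) = 11.1 points, at least 10% of any baseline. And these two scales may not capture every hormone syndrome, since the biochemical outcome allows for hormones other than 5-HIAA.

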## **Introduction**

Neuroendocrine tumors (NET) are rare neoplasms, but with increasing incidence and prevalence in the last decades. In more than half of the cases, they present metastatic and incurable at diagnosis. Few effective therapies are approved for these tumors (somatostatin analogues, everolimus, and sunitinib), none have demonstrated gains in overall survival, and none is approved in the Brazilian public health system (SUS).

Well-differentiated NET express, in more than 80% of the cases, somatostatin receptors. Somatostatin analogues, lanreotide or octreotide, have anti-proliferative and anti-secretory activity, and, frequently, are considered the first-line treatment in the metastatic setting. Somatostatin receptors expression, through scintigraphy scan marked with radionuclide and octreotate (Octreoscan©) or positron emission tomography labelled with Ga (Ga-PET-CT), is mandatory to effectively indicate the treatment with Lutetium^177 radionuclide. The NETTER-1 study demonstrated the efficacy of Lutetium^177, a type of peptide receptor radionuclide therapy (PRRT), in combination with long-acting releasing (LAR) octreotide 30 mg in second-line, with progression-free survival of approximately 40 months versus 8.5 months for the group treated only with LAR octreotide monthly in patients with midgut NET metastatic (HR: 0.20;  $p < 0.0001$ ). The NETTER-1 study established one more therapeutic strategy to NET, the PRRT.

However, invariably, metastatic NET patients develop disease progression to standard treatment. Different chemotherapeutic regimens (FOLFOX, cisplatin/etoposide, cisplatin/irinotecan, capecitabine/oxaliplatin, and capecitabine/temozolomide), hepatic debulking surgery, and interferon alpha are used based on small phase 2 trials and/or retrospectives studies. In the Brazilian consensus of NET, these treatment modalities, even with low evidence level, are recommended when there are no other effective treatments available. Although some patients could benefit from these therapeutic options, the results relating to tumor response and quality of life tend to be modest and the toxicity significant (Table 1). Therefore, new treatment should be investigated in this context.

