Retrospective studies demonstrated that 50% to 60% of patients with gastroenteropancreatic (GEP) NET may have tumors with positive expression of MIBG-I, especially those with well-differentiated G1 and functioning tumors (producers of amines that cause clinical symptoms, such as carcinoid syndrome). Based on this information, it is intuitive to investigate the treatment with MIBG-I in other types of NET than PggF. In the largest series of cases, 211 patients with GEP or pulmonary NET treated with MIBG-I from 1994 to 2014, at the maximum dose of 18,500 MBq, had a median survival of 29 months since the start of treatment, 71% of clinical improvement with a median duration of 12 months and 20% with radiological response (80% disease control). Retrospective study with 38 patients with progressive NET GEP treated with a single dose of 7,400 MBq demonstrated 75% of radiological control of disease (3% of objective response), 63% with improvement of symptoms and median overall survival of 4 years. Toxicity was manageable, with 10% of transient neutropenia or thrombocytopenia and without complications. In another retrospective study of 38 patients with NET (most GEP NET [25 midgut]; one patient with lung NET and 4 with PggF), MIBG-I was administered at a dose of 5.5 GBq in three cycles at intervals of 10 to 12 weeks. The median progression-free survival was 13 months, the median overall survival was 48 months and the disease control rate was 65% (3 objective responses and 22 with stable disease). In terms of tolerability, only 2 patients (5%) had grade 3 myelotoxicity, which prevented the third application of MIBG-I. Another

retrospective study with 25 metastatic (17 NET) patients treated with MIBG-I with a cumulative dose of 27.7 GBq (751mCi) showed improvement in symptoms in 80% of cases and 48% of radiological response by WHO criteria. The median overall survival was 17 months since the last dose of MIBG-I, with a 5-year survival rate of 59%. Other studies have assessed the role of MIBG-I in controlling symptoms of refractory carcinoid syndrome. A retrospective study from the 1990s reported improvement in carcinoid symptoms in 14 out of 30 patients, with a median duration of 8 months.

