### **Secondary:**

1- Disease control rate (DCR). Defined by absence of radiological progression in conventional imaging examinations by RECIST 1.1 at 3 months after the end of treatment. For patients with functioning syndrome, beside radiological DCR, patients should have improved in at least 10% of the baseline score of quality-of-life (EORTC QLQ-GINET21) and stability or decrease in tumor markers.

2- Progression-free survival. Defined by time from day 1 cycle 1 to death from any cause or radiological progression by RECIST 1.1, whichever occurs first. Patients alive and without progression at the time of study analysis will be censored for time-to-event analysis.

3- Radiological response rate. Assessed by RECIST 1.1 criteria.

4- Rate of Biochemical response. Defined by at least 30 percent drop in the tumor marker (24-hour urine 5-hydroxyindoleacetic acid (5-HIAA) and/or specific hormone), if functioning syndrome, at any time of treatment in relation to pre-treatment value.

5- Quality of life. Assessed by the EORTC QLQ-C30 and QLQ-GINET21; both available in Brazilian Portuguese. Improvement of at least 10% in the baseline score at 3 and 6 months after the end of the treatment will be considered clinically meaningful. Improvement by 10% of the baseline score at 3 and 6 months will be considered clinically meaningful.

6- Incidence of Treatment-related Adverse Events. Frequency of adverse events of grades 2 or more by Common Adverse Event Toxicity Criteria (CTCAE) version 5.0.

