#### **Inclusion criteria**

- Age greater than or equal to 18 years.
- Well-differentiated metastatic NET from GEP, unknown primary with hepatic metastases or advanced/metastatic lung, inoperable, with no possibility of curative treatment.
- MIBG-I scintigraphy with positive expression in at least one lesion that presents significant uptake and compatible with therapeutic effectiveness.

- Disease with radiological progression (at least 10% tumor volume growth) in the last 12 months or with clinical and biochemical progression to functional NET according to clinical judgment.
- Progression or intolerance to previous standard treatments according to scenario (private [somatostatin analogue, everolimus] or public [somatostatin analogue]).
- Measurable disease.
- ECOG performance scale 0 to 2.
- Adequate organic function as defined by the following criteria:
  - Aspartate serum aminotransferase (AST), alanine serum aminotransferase (ALT)  $\leq$  2.5 times the upper limit of normal of the local laboratory (ULN-LL);
  - Total serum bilirubin  $\leq$  2.0 x ULN-LL;
  - Absolute neutrophil count  $\geq$  1,500/mm^3;
  - Platelet count  $\geq$  100,000/mm^3;
  - Hemoglobin  $\geq$  9.0 g/dL;
  - Estimated creatinine clearance using the MDRD equation  $\geq$  60ml/min
  - Informed consent form signed by the patient or legal representative.

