#### Effectiveness and Follow-up Assessments:

For evaluation of efficacy, patients will undergo imaging tests (chest, abdomen and pelvis tomography or abdomen and pelvis resonance) at baseline (within 8 weeks of starting treatment) and every 12 weeks (+/- 5 days) until progression or withdrawal from the study. Patients will also be evaluated for signs and symptoms that may be related to disease progression. Patients who present clinical progression, according to the investigator's judgment, but without radiological progression, will be able to discontinue the treatment and continue the image evaluation until progression; however, if new treatment is instituted, the last date of receipt of MIBG-I will be the censorship date in the progression-free survival analysis.

After documenting progression or leaving the study for other reasons, patients will be followed up by the investigator or another oncologist from the Clinical Oncology team for symptom control, image monitoring and possible future therapies. The patient continues to be cared for at the A.C.Camargo Cancer Center, if desired.

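### In functional NET, clinical/biochemical control and biochemical response still count when an anti-secretory drug was started or raised after baseline

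*Combined protocol and SAP*

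**What the plan says.** Under Objectives, Primary, the second objective is "Control of clinical/biochemical (functional NET) at 6 months after the end of treatment". Outcomes, Primary puts this into the disease control rate (DCR): besides freedom from RECIST progression, for functioning syndromes "patients should have improved in at least 10% of the baseline score of quality-of-life (EORTC QLQ-GINET21) and stability or decrease in tumor markers". Outcomes, Secondary, item 1 repeats the rule at 3 months. Item 4 defines biochemical response as a marker fall of at least 30% "at any time of treatment in relation to pre-treatment value".

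None of these definitions mentions concomitant anti-secretory drugs, and the protocol has no section on permitted, prohibited or rescue medication. The nearest rules are these:

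- Exclusion Criteria set a three-week gap after cancer therapy. This acts at entry only and does not name analogues.
- The safety assessments note medication use at the 15-day visits, which after treatment continue only until adverse effects resolve. The database items listed under Study design include previous treatments but no concomitant drugs, and Table 2 has no medication row.
- The criteria for suspending treatment list clinical progression and need for new cancer therapy as reasons why a patient may stop MIBG.
- Effectiveness and Follow-up Assessments covers new treatment after clinical progression without radiological progression: the last MIBG date "will be the censorship date in the progression-free survival analysis".
- The Statistical plan says that analyses are by intention to treat, and counts patients who do not respond as non-responders in the quality-of-life analysis.

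**The concern.** The protocol itself supplies the mechanism. The Introduction says that somatostatin analogues "have anti-proliferative and anti-secretory activity" and describes functioning tumours as "producers of amines that cause clinical symptoms, such as carcinoid syndrome". Quality of Life Assessment says that the GINET21 covers, among other domains, "common symptoms in patients with NET, such as gastrointestinal and endocrine". One dose increase can therefore improve the questionnaire score and lower the marker together. There is no control arm to separate that effect from MIBG.

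The situation is plausible here. The Inclusion criteria admit functional patients on clinical and biochemical progression, which is when symptom treatment tends to be adjusted. They do not say whether a prior analogue is stopped or continued. The two baselines can also be taken at different times: the marker up to 8 weeks before the first dose, the GINET21 within 4 days of treatment. A dose change between them would put them on different background treatment.

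At stake are a primary objective and a secondary rate. The secondary rate has no radiological condition, so a raised anti-secretory dose alone could produce a biochemical response.

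**Working it through.** **1. The plan's sample size.** Inputs from the Statistical plan: DCR 40% against 67%, two-sided 10% error, 80% power, 10% loss.

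n = [(1.645 × √(0.40 × 0.60) + 0.842 × √(0.67 × 0.33)) / 0.27]² = 19.8, so 20. Then 20 × 1.1 = 22, the stated figure (20/0.9 would give 23). This point does not dispute N.

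**2. Does any rule assign an outcome?** Take a functional patient with no RECIST progression whose analogue dose was raised after baseline and who then improves.

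- The entry washout is past.
- The suspension criteria and the censoring rule affect MIBG dosing and PFS only.
- Intention to treat settles who is analysed. It does not expressly say whether control reached on a raised dose is MIBG control.

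Read literally, the patient meets the component.

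**3. Size per patient.** The functional share is not in the documents. Assume 30% to 60% of 22: 0.3 × 22 = 6.6 (about 7) and 0.6 × 22 = 13.2 (about 13). One patient who meets the criterion only through escalation moves:

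- the functional-subgroup control or biochemical response rate by 1/13 = 7.7 to 1/7 = 14.3 points;
- the composite DCR by 1/22 = 4.5 points.

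**4. Composite DCR, illustration.** Let R be radiological control (0.40, the plan's null), f the functional share, q the share of radiologically controlled functional patients who would fail the component without escalation, and e the share of those who meet it through escalation. The values of f, q and e are all assumed.

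Without escalation: R(1 − fq). With escalation: R(1 − fq(1 − e)).

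- Low case (0.3, 0.3, 0.25): 0.364 to 0.373, or 22 × 0.009 = 0.2 patients.
- High case (0.6, 0.5, 0.5): 0.280 to 0.340, or 22 × 0.060 = 1.3 patients.
- Limit e = 1: the composite equals R = 0.40.

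**5. Primary test.** The plan states no cutoff. With exact binomial tails at n = 22 and p = 0.40, P(X ≥ 13) = 0.055 and P(X ≥ 14) = 0.0215, so 14 is the smallest count with an upper tail of at most 5%. Chance of 14 or more:

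- Low case: 0.0086 to 0.0109.
- High case: 0.0005 to 0.0043.
- Limit: 0.0215.

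**The case against.** Several objections carry weight.

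- **The route is narrow.** Entry requires "Progression or intolerance to previous standard treatments according to scenario (private [somatostatin analogue, everolimus] or public [somatostatin analogue", so a first analogue start is unlikely. To be miscounted in DCR, a patient must be free of progression, improve by 10% over baseline, have a marker no worse than baseline, and owe this to a drug still escalated 6 months after treatment. This stands. It narrows the gap mainly to sustained dose increases and added drugs, though not for biochemical response, which needs only a 30% fall.
- **Medication is already noted.** True at baseline and at the 15-day visits, but those may end before the 6-month reading, and nothing links the record to an endpoint.
- **Intention to treat can mean counting outcomes whatever drugs follow.** That is a legitimate reading, and it belongs in the report as a sensitivity analysis. As the only analysis, it cannot support attributing symptom and marker control to MIBG.
- **Describing drug use might be enough in a 22-patient phase 2 trial.** It would help, but the listed database items would not support it at present.

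A reader might also infer that escalation inflates the primary test's false-positive rate. Suppose true composite DCR is 40%, and a share q of functional patients who would otherwise fail is turned into successes. The rate becomes 0.40 + f × 0.60 × q, and with a rule of 13 of 22 the chance of a positive result rises from 0.055 to 0.073 (f = 0.25, q = 0.10) or 0.232 (f = 0.75, q = 0.20). The documents do not support that reading. It converts patients who failed on imaging, and an anti-secretory drug supplying the clinical/biochemical part cannot do that. The 40% also comes from placebo arms such as RADIANT-4, which the reference list gives as a trial in non-functional NET.

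**Conclusion.** The concern holds for clinical/biochemical control in functional NET and for biochemical response. Followed literally, the plan credits MIBG with improvement caused by an anti-secretory drug started or raised after baseline, and the database as listed could not correct this later.

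The total bias cannot be derived, because neither the functional share nor the escalation rate is given. The per-patient effect on a functional-subgroup rate is 7.7 to 14.3 points under the assumed 30% to 60% share. The primary DCR test is not made anti-conservative if the 40% null is radiological: composite DCR cannot exceed radiological DCR, and with a 14-of-22 rule the chance of a false positive stays at or below 2.15%. The change should be made, but the gap does not undermine the radiological result.

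**What to change.** 1. In Exclusion Criteria, state that a stable somatostatin analogue for symptom control is not cancer therapy for the three-week rule. Define the reference dose as the dose in use when the baseline marker and GINET21 were taken. If the analogue was stopped before baseline, the reference dose is zero and restarting it counts as a start. Without this, a patient measured off the drug and then restarted would bring the same bias back.
2. In Outcomes, Primary and Secondary items 1 and 4, add a rule for functional patients. It applies to a patient on a newly started anti-secretory drug, or on a dose above the reference, at the 3- or 6-month reading or when the 30% fall is measured. That patient does not meet the clinical/biochemical component and is not a biochemical responder on that value. Continuing the reference dose is not a failure, and neither is a brief increase already reversed.
3. Report radiological DCR separately, the number failing only through this rule, and a sensitivity analysis counting outcomes regardless of escalation.
4. Extend the medication record to the 12-week follow-up visits, and enter anti-secretory drug and dose in the database.

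Cost: protocol wording and a database entry at existing visits, with N unchanged. A patient whose dose changed between the two baseline measurements may need a repeat marker. Control and response rates may come out slightly lower, because some escalated patients would have met the criterion anyway. The sensitivity analysis shows how much.
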